5.1.5 Toxicity management and dose modifications

If a patient experiences a CTCAE ≥ grade 3 and/or unacceptable toxicity including a DLT not attributable to the disease or disease-related processes under investigation, where the investigator considers the AE of concern to be specifically associated with DZD9008, dosing should be interrupted and supportive therapy will be administered as required in accordance with local practice/guidelines.

If the toxicity does not resolve to \leq CTCAE grade 2 within 21 days, then the patient should be withdrawn from the study and observed until resolution of the toxicity.

If the dose reduction is due to drug related AE, the dose is not allowed to escalate back to the original level after AEs resolve.

On resolution of toxicity within 21 days during treatment, DZD9008 may be restarted at the same dose or a lower dose:

Date: July 24,2023

- If a further episode of the same AE subsequently requires dose interruption, patient should restart at one dose level lower (except cohort 1 dose, restart at cohort 1 dose level). (Refer to Table 3). For cohort 2 of Part B, the dose could be reduced to 200 mg and then 150 mg if needed; for cohort 1 of Part B, dose could be reduced to 150 mg).
- If a different AE subsequently requires dose interruption or no prior AE related dose interruption, DZD9008 may restart at same dose level or one dose level lower (unless in Part A Cohort 1, when restart will be at Cohort 1 dose) on improvement of the AE at the discretion of the Investigator.
- Patients who are at the lowest possible dose, and who have demonstrated clinical benefit and an acceptable recovering of AEs to the dose interruption may be permitted to restart at the lowest dose level at the discretion of the Investigator.
- After a second occurrence of CTCAE grade 4 AE, patient must be permanently withdrawn from study treatment (France and Canada only).

Patients with QTc prolongation fulfilling the following criteria (i.e., confirmed QTc prolongation to > 500 msec absolute or a > 60 msec increase from baseline) should have study treatment interrupted and regular ECGs performed until resolution to baseline. If the toxicity does not resolve to \le grade 1 within 3 weeks, the patient will be permanently withdrawn from study treatment. Patients who develop QTc interval prolongation with signs/symptoms of life-threatening arrhythmia will permanently discontinue DZD9008.

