5.2.2.3 Ocular surface effects

Full ophthalmic assessment, including slit lamp examination, will be performed at screening and should be repeated if a patient experiences any visual symptoms (including blurring of vision), with additional tests if clinically indicated. Any clinically significant findings, including those confirmed by the ophthalmologist must be reported as an AE. Photographs may be performed to record any clinically significant findings. Ophthalmology examination results should be collected in the eCRF. Any patient developing corneal ulceration will be permanently discontinued from study treatment and should be followed regularly until resolution of the event.

Patients who wear contact lenses will be advised to discontinue wearing lenses if they have any mild to moderate eye symptoms (CTCAE grade \leq 2) while receiving treatment with DZD9008 until at least one week after symptoms have resolved. If a patient has recurrence of eye symptoms or experiencing any severe (CTCAE grade \geq 3) ocular events they should discontinue wearing their contact lenses until at least one week after treatment with DZD9008 is permanently discontinued. Patients should not use any eye drops or ointment for treatment of eye symptoms has been permanently discontinued. Patient will be advised to consult the investigator promptly if they have any concerns.

Date: July 24,2023

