5.3 Discontinuation of investigational product and withdrawal from the study

Patients may withdraw from the study at any time, without prejudice to further treatment and independent of any decision concerning participation in other aspects of the main study. Procedures for withdrawal from the exploratory research are outlined in Section 5.3.2.

Patients may be discontinued from investigational product in the following situations:

- Patient decision. The patient is at any time free to withdraw his/her participation in the study, without prejudice
- Adverse events

• Severe non-compliance to this protocol as judged by the investigator and/or Study Team

- Confirmed disease progression as per RECIST 1.1, unless, in the opinion of the investigator, the patient is still deriving clinical benefit. For France and Canada only: fulfil the following criteria: (a) Absence of clinical symptoms and signs of disease progression (including clinically significant worsening of laboratory values); (b) Stable ECOG PS; (c) Absence of rapid progression of disease or of progressive tumor at critical anatomical sites that requires urgent alternative medical intervention; (d) Investigators must inform subjects that this practice is not considered standard in the treatment of cancer.
- Patients incorrectly initiated on investigational product (Section 5.3.1)
- Pregnancy

Patients who withdraw from the study but are evaluable for safety assessment in Part A escalation will not be replaced. Any patient that is not evaluable in Part A escalation will be replaced to ensure a minimum number of evaluable patients. Once study medication is permanently discontinued it cannot be restarted.

In Part A expansion and Part B, any patient who discontinues study treatment for reasons other than disease progression should have RECIST assessment performed as scheduled in Table 13 and Table 14 of the protocol until disease progression is documented or death occurs, or consent is withdrawn. Study procedure related SAEs and anti-cancer treatment must be captured until the patient no longer has RECIST 1.1 tumor assessment (disease progression or permanent withdrawal from the study).

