6.8 Anti-tumor efficacy

6.8.1 Tumor assessments

6.8.1.1 Imaging assessment

RECIST 1.1 criteria will be used to assess tumor response to treatment by determining Objective Response rate (ORR), Disease Control Rate (DCR), Duration of Response (DOR) and Progression Free Survival (PFS). The RECIST 1.1 guidelines for measurable, non-measurable, target and non-target lesions and the objective tumor response criteria (complete response, partial response, stable disease or progression of disease) will be used for the assessment of tumors according to Appendix F.

Imaging assessments will be performed using CT scan or MRI to assess extracranial lesions, such as chest, abdomen (including liver and adrenal glands). MRI is the preferred method for analyzing the brain lesion if brain metastasis presents at baseline (within 28 days of treatments start, ideally as close as possible to the start of study treatment), on Cycle 3 Day 1 (\pm 7 days) and then every 6 weeks \pm 7 days until objective disease progression or withdrawal from study. Contrast-enhanced CT can be used if MRI is not feasible. In addition, additional areas should be investigated based on the signs and symptoms of the patient. Any other sites at which new disease is suspected should also be appropriately imaged. If an unscheduled assessment is performed and the patient has not progressed, every attempt should be made to perform the subsequent assessments at their scheduled visits.

Categorization of objective tumor response assessment will be based on the RECIST 1.1: CR (complete response), PR (partial response), SD (stable disease) and PD (progression of disease). Target lesion (TL) progression will be calculated in comparison to when the tumor burden is at a minimum (i.e. smallest sum of diameters previously recorded on study). In the absence of progression, tumor response (CR, PR, SD) will be calculated in comparison to the baseline

Date: July 24,2023

tumor measurements obtained before starting treatment. For objective response rate (ORR), a visit response of CR or PR must be confirmed by a later scan conducted at the next scheduled visit and no less than 4 weeks after the initial visit response of CR or PR.

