- Provide guidance on when to perform follow-up ophthalmic assessments
- Promote consistency of assessment across the study.

Some key points for Ophthalmic Guidance

- It is important that patients are fully informed that ophthalmic event may occur during treatment with DZD9008.
- DZD9008 should not be administered on the first scheduled day if the patient has any clinically significant eye symptoms.
- Patients should be encouraged to report any instance of ophthalmic symptoms and/or vision changes to allow the appropriate treatment to be initiated. Symptoms may include:
 - o Burning/ itching/ irritation/ smarting
 - o Redness with / without discharge
 - o Blurred vision
 - Light sensitivity
- Patients who wear contact lenses must discontinue wearing them if they have any mild to moderate eye symptoms (CTCAE grade ≤ 2) until at least one week after symptoms have been resolved.
- Only after agreement with the investigator, patients may use eye drops or ointment for treatment of eye symptoms.
- If a patient has a recurrence of eye symptoms or experiences any severe (CTCAE grade ≥ 3) ocular events they must discontinue wearing their contact lenses until at least one week after treatment with DZD9008 is permanently discontinued.
- Ulcerative events must result in permanent discontinuation from study.
- Patients with ophthalmic AEs of CTCAE grade≥ 3 (For France and Canada only: CTCAE grade ≥ 2) or eye symptoms that are clinically significant and/or persistent (>7 days) should be referred to the ophthalmologist. For example:
 - o Deterioration in near or distant visual activity by more than one level
 - o Persistence or worsening of:
 - Burning/irritation/smarting
 - Itching
 - Redness with or without discharge
 - Light sensitivity (photophobia)

Date: July 24,2023

Blurred vision

• Ophthalmology examination findings should be documented in the patient's notes and reported to Dizal team if required.

Baseline assessment

- Full ophthalmological assessment, including slit lamp examination performed by an ophthalmologist (or appropriately qualified individual)
- Date of assessment should be recorded on the CRF
- Results should be recorded in the patients' notes

Follow-up assessment

- If the patient reports any eye symptoms during treatment with DZD9008 or if signs are
 observed during a study visit, the investigator should perform a clinical examination
 including a repeat best corrected near and distant visual acuity assessment if appropriate

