2.1.1 Primary Objective and Estimand

Objectives	Endpoint/Estimand Description	
To evaluate anti-tumor activity of DZD9008 in advanced NSCLC patients with EGFR Exon20ins at defined dose(s) by assessment of Objective Response Rate (ORR)	Endpoint: Objective Response Rate (ORR) according to Response Evaluation Criteria in Solid Tumors (RECIST) version 1.1 evaluated by an Independent Review Committee (IRC), where confirmation of response is required.	
	Estimand Description:	
	Treatment: DZD9008 200 mg or 300 mg QD.	
	Population: Full Analysis Set (FAS) will be used for analysis, including all the NSCLC patients with documented EGFR Exon20ins mutations in tumor tissue, who were previously treated with platinumbased chemotherapy, received at least one dose of DZD9008, have at least one measurable lesion at baseline as identified by IRC.	
	Variable: Binary variable indicating whether patient is a responder who achieved confirmed complete response (CR) or partial response (PR) prior to progressive disease (PD), as evaluated by IRC according to RECIST 1.1;	

Objectives	Endpoint/Estimand Description	
	Intercurrent Event with Strategy:	
	PD evaluated by IRC	
	While on treatment strategy: the intercurrent event is already captured in the variable definition	
	Treatment Discontinuation due to reason other than PD evaluated by IRC	
	Treatment policy strategy: Intercurrent event is ignored, tumor response data irrespective of treatment discontinuation are considered in analysis.	
	New Anticancer Therapy	
	While on treatment strategy: Only the tumor response data prior to start of the new anticancer therapy are of interest.	
	Population-level Summary: Confirmed ORR, which is defined as the proportion of responders.	

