3	No progression at the time of data cut-off/discontinuation from the study	Censored/ Date of last visit with evaluable* radiological tumor assessment prior to data cut-off or discontinuation from the study.	Same as primary analysis
4	Treatment discontinuation for reason other than radiological PD	Data after discontinuation of treatment will be included when determining the time to progression	Same as primary analysis
5	New anticancer treatment started	Data after new anticancer treatment will be included when determining the time to progression	Same as primary analysis
6	Death between scheduled tumor assessment visits	Event/ Date of death	Same as primary analysis
7	Death or progression after two or more missed tumor assessment visit**	Censored/Date of last evaluable* radiological tumor assessment with documented non-progression	Event/Date of first radiological progression or death
8	No baseline or any post-baseline tumor assessments and died within two tumor assessment visits (13 weeks) from date of first dose	Event/Date of death	Same as primary analysis

^{*}Evaluable tumor assessment is a radiologic assessment of CR, PR, SD, non-CR/non-PD or PD.

^{**}Interval between the death/progression and the last evaluable tumor assessment before missed visits is longer than 14 weeks (98 days).

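### Some toxicity rules take patients out of the study where others take them off treatment, so a site reading them literally could stop scans that the primary estimand needs

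*Protocol*

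**What the plan says.** Two kinds of exit appear for patients who stop because of toxicity.

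- Leaving the study. In Protocol 5.1.5, a patient whose drug-related toxicity has not returned to grade 2 or lower within 21 days: "then the patient should be withdrawn from the study and observed until resolution of the toxicity". In Appendix I, ophthalmic guidance: "Ulcerative events must result in permanent discontinuation from study".
- Leaving treatment. In the QTc rule of 5.1.5: "the patient will be permanently withdrawn from study treatment". The rule in 5.1.5 on a second grade 4 event (France and Canada) also refers to study treatment. For corneal ulceration, 5.2.2.3 says: "Any patient developing corneal ulceration will be permanently discontinued from study treatment". The statements in 5.1.5 and 6.3.5.4 on not restarting after corneal ulceration refer to study treatment as well.

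The follow-up rules also differ among themselves.

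- Protocol 6.8.1.1 runs imaging "until objective disease progression or withdrawal from study". A parenthesis in 5.3 likewise gives progression or permanent withdrawal from the study as the end of RECIST assessment.
- Appendix F stops follow-up scans at discontinuation of study treatment or withdrawal of consent.
- Protocol 5.3 says of Part A expansion and Part B: "any patient who discontinues study treatment for reasons other than disease progression should have RECIST assessment performed as scheduled", until progression, death or withdrawn consent. Protocol 6.3.6.2 and SAP 2.2 agree.
- Table 14, footnote k, collects survival status after progression or withdrawal from treatment.

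In the SAP, the primary estimand (2.1.1) handles a stop for reasons other than progression thus: "Treatment policy strategy: Intercurrent event is ignored, tumor response data irrespective of treatment discontinuation are considered in analysis". For a patient without progression who leaves the study, Table 2 row 3 of the PFS section reads: "Censored/ Date of last visit with evaluable* radiological tumor assessment prior to data cut-off or discontinuation from the study".

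**The concern.** The title of Protocol 5.3 itself separates discontinuing the product from withdrawing from the study, and 5.3.2, on consent withdrawal, describes the study as covering both product and assessments. A site could therefore take the 21-day sentence in 5.1.5 at its word, apply the stop rule in 6.8.1.1, and cease scanning once the toxicity had resolved. The patients affected would be selected by toxicity.

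Three results could suffer.

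- Confirmed ORR by IRC: a response not yet confirmed would count as a non-response, although the estimand asks for scans after the stop.
- DoR and PFS: patients would be censored at their last evaluable scan, close to the time they stop the drug. If progression is faster off drug, this censoring is informative and the Kaplan-Meier curves are too high.
- OS: survival contact could lapse, although footnote k of Table 14 points the other way.

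**Working it through.** Step 1: which rule governs. A Part B patient stops for a toxicity unresolved at 21 days.

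- Route A reads 5.1.5 as a treatment stop. Sections 5.3 and 6.3.6.2 apply and scans continue to progression. Loss from this cause is zero.
- Route B reads 5.1.5 literally. The patient has left the study and 6.8.1.1 ends imaging. The rule in 5.3 is written for patients who discontinue treatment and does not say which sentence prevails.
- Appendix F would end scans even on Route A, so changing the word in 5.1.5 alone leaves a conflict.

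Step 2: reproduce the design. Inputs: 7 or fewer responses of 39 stops the cohort (Protocol 5.3.3); null 0.17 (7.9.7.1); expected ORR 0.30 and n = 103 (SAP 2.4); one-sided 0.0125 (Protocol 7.2.2). Power of 80% appears only in the version history. The final threshold r is blacked out, so I took the smallest r that keeps the level:

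P(reject | p) = Σ over x = 8 to 39 of Bin(x; 39, p) × P(Bin(64, p) ≥ r − x)

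- r = 26: 0.0196 at p = 0.17, too large.
- r = 27: 0.0111 at p = 0.17; power 0.801 at p = 0.30.

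The stated design reproduces.

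Step 3: lost confirmation. Assume a share q of would-be responders loses the confirming scan. They stay in the FAS, so the effective ORR is 0.30 × (1 − q), with r = 27:

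| q (assumed) | Effective ORR | Power |
|---|---|---|
| 0 | 0.300 | 0.801 |
| 2% | 0.294 | 0.765 |
| 5% | 0.285 | 0.702 |
| 10% | 0.270 | 0.581 |

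Step 4: duration of response at 12 months. Assumptions: exponential DoR with median 9 months, so λ = ln 2 / 9 = 0.0770; a share f of responders leaves at a time u uniform on 0.5 to 6 months; the hazard is multiplied by k afterwards. Censoring leavers at u makes Kaplan-Meier estimate the on-drug curve, exp(−12λ) = 39.7%. The true value is (1 − f) × 39.7% + f × L, where L is the mean over u of exp(−λ[u + k(12 − u)]). L = 20.4% for k = 2 and 10.6% for k = 3.

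Bias = f × (39.7% − L):

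| f | k | Kaplan-Meier | True | Bias (points) |
|---|---|---|---|---|
| any | 1 | 39.7% | 39.7% | 0 |
| 2% | 2 | 39.7% | 39.3% | 0.4 |
| 5% | 2 | 39.7% | 38.7% | 1.0 |
| 10% | 2 | 39.7% | 37.8% | 1.9 |
| 15% | 3 | 39.7% | 35.3% | 4.4 |

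**The case against.** The strongest reply is that the plan already requires the follow-up. Protocol 5.3 lists adverse events among the reasons for stopping the product and does not list toxicity among the reasons for ending scans. Protocol 6.3.6.2 and SAP 2.2 repeat the scan rule, and SAP Table 2 row 4 keeps data collected after the treatment stop. This stands. A reader might infer from 5.1.5 that confirmatory scans and DoR, PFS and OS follow-up are actually lost. The documents do not support that: they contain both instructions and do not say which one sites follow. Nor do they support the inference that 5.1.5 ends survival follow-up. That sentence does not mention survival, and footnote k of Table 14 continues it.

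The ORR harm is also narrow. An exit between the first scan (about week 6) and the second (about week 12) means an interruption that began at about weeks 3 to 9. SAP 4.2.1 asks for only 28 days between the two response visits, and IRC receives unscheduled scans, so some such patients could still be confirmed. An unconfirmed week-6 PR followed by no evaluable scan is scored SD under SAP Table 1, because the earliest permitted scan (day 36) meets the 35-day minimum. The error lowers ORR, so it does not inflate type I error. That 27 responses pass and 26 fail shows only that the test has a boundary; it says nothing about how often this exit occurs.

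Finally, DoR and PFS are descriptive, and SAP 5.6.1 makes the 200 mg ORR statistics descriptive, which weakens any argument from a difference between arms.

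What remains is that 5.3 does not clearly override 5.1.5. The patient in question is described as having left the study, and 6.8.1.1 and the parenthesis in 5.3 treat that as the end of RECIST assessment.

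**Conclusion.** The contradiction is real and should be removed. Protocol 5.1.5 and Appendix I use study-exit wording where other toxicity rules use treatment-exit wording, and 6.8.1.1 attaches a stop to imaging at study exit. A site reading 5.1.5 literally could stop the scans that 5.3, 6.3.6.2, SAP 2.2 and the treatment-policy estimand require.

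If that happened, ORR would be biased downward. DoR and PFS would be biased upward only if progression is faster off drug. OS could be incomplete, with the text of Table 14 against that outcome.

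The size is illustrative throughout. The documents give no rate for this exit and no hazard after stopping, and the 9-month median DoR is likewise assumed. Loss is zero where sites follow 5.3. At assumed confirmation losses of 2% to 10%, power is 0.76 to 0.58 against 0.80. For 12-month DoR, the overstatement is about 0.4 points (2% leave) to about 2 points (10% leave) with a doubled hazard, about 4 points with 15% leaving and a tripled hazard, and nil with an unchanged hazard.

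This is a risk of informative loss to follow-up arising from inconsistent wording. It is not a demonstrated loss.

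**What to change.** Reconcile Protocol 5.1.5, Appendix I (ulcerative events), 6.8.1.1 and Appendix F with 5.3, 6.3.6.2 and Table 14 footnote k, and bring the parenthesis in 5.3 into line. State once, with cross-references, that for Part B patients who stop the drug because of toxicity:

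- RECIST assessments continue on schedule until progression, death or withdrawal of consent;
- survival follow-up continues unless consent is withdrawn.

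Appendix F must be included because it would otherwise still end scans at treatment discontinuation. The 21-day rule and the other toxicity and treatment-stopping rules are for the sponsor to settle; nothing here proposes changing them.

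The cost is a wording change in the next amendment and a letter to sites. No scan is added beyond those that 5.3 and 6.3.6.2 already require, and n = 103 per arm, the significance level and the design power are unchanged.

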5.1.6 Assessment timing if dosing is interrupted

If a patient misses any doses of DZD9008 during the 28-day evaluation period of Cycle 1 of Part A, please contact the Dizal Study Team for advice regarding the evaluability of the patient and appropriate timing of the PK assessments. All other assessments, including laboratory safety assessments, vital signs and RECIST should continue to be performed as per study plan, relative to the baseline assessments.

Figure 3 Dose modification for toxicity related to DZD9008

Date: July 24,2023

5.1.7 Duration of treatment

Patients may continue on treatment with DZD9008 until RECIST 1.1 defined disease progression or until treatment discontinuation criteria are met or withdrawal of consent, or 2 years post study completion or first indication market available (if patients are still on treatment when study completion).

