After database lock, there may be some patients remaining on study treatment. For these patients who are continuing to receive the study treatment, Sponsor will collect information during the treatment period and for 28 days after last dose on SAEs, death (including those due to disease progression), discontinuation due to AEs/SAEs and drug accountability.

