5.5 Post study access to study treatment

Any patients still receiving investigational product at the time of end of the study will be able to continue to receive DZD9008 if in the opinion of investigator they continue deriving clinical benefit with agreement with Dizal study physician. Re-consent is required. Such patients will continue to be monitored for safety assessments until DZD9008 is discontinued. These patients will then be followed up for treatment-related Serious Adverse Events up to 28 days after the last dose of investigational product. A CSR addendum will be prepared to summarize any additional safety data collected.

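### Section 5.5 follows only treatment-related SAEs in the 28 days after last dose, narrower than sections 5.3 and 6.4.4, and it is not reconciled with section 5.1.7 on when post-study treatment ends

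*Protocol*

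**What the plan says.** **Safety follow-up after the last dose.** Protocol section 5.5 covers patients still on drug when the study ends. While they are dosed, "Such patients will continue to be monitored for safety assessments until DZD9008 is discontinued". After that they are "followed up for treatment-related Serious Adverse Events up to 28 days after the last dose of investigational product", and a CSR addendum summarises whatever further safety data were collected.

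The closing paragraph of section 5.3 covers patients still on treatment after database lock. There the "Sponsor will collect information during the treatment period and for 28 days after last dose on SAEs, death (including those due to disease progression"), together with discontinuations due to AEs or SAEs and drug accountability.

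Two general rules apply as well. Section 6.4.3.1 defines the follow-up period as 28 days after discontinuation and has SAEs in that period reported in the normal way. Section 6.4.4 requires every SAE to be reported, related or not.

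**End of post-study treatment.** Section 5.1.7 lists, among the events that end treatment, "or 2 years post study completion or first indication market available (if patients are still on treatment when study completion"). Section 5.5 says such patients "will be able to continue to receive DZD9008 if in the opinion of investigator they continue deriving clinical benefit". Two further conditions apply: the sponsor's physician has to agree, and the patient has to consent again. It gives no date and no market condition, and it does not mention 5.1.7.

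**The concern.** A patient dosed beyond both database lock and the end of the study falls under sections 5.3 and 5.5 together, and the two ask for different data after the last dose. A site that works from 5.5 would have no instruction there to send an SAE it judged unrelated, or a death not tied to a related SAE. These are the patients with the longest exposure, and investigator causality in an open-label study is a judgement. A filter on relatedness at the point of collection cannot be undone at analysis.

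The duration wording raises a different problem. Section 5.5 requires re-consent, so the patient has to be told how long supply may continue. A site reading 5.1.7 and a site reading 5.5 could give different answers.

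**Working it through.** No sample size, power or event count is involved, and the plan states no figure to reproduce. The check is a comparison of the current text.

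**1. Who is covered.** Section 5.3 is triggered by database lock. Section 5.5 is triggered by the end of the study, which Appendix E defines as the last visit of the last patient. The triggers differ, but a patient still dosed after both meets both.

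**2. While on drug.** Section 5.3 collects during treatment, and 5.5 continues safety monitoring until the drug stops. The treatment-related restriction in 5.5 is attached only to the period after the last dose, so there is no narrowing here.

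**3. After the last dose.** The window is 28 days in both sections. Only the scope differs:

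- Section 5.3: SAEs with no causality condition; deaths, including those from progression; discontinuations due to AEs or SAEs; drug accountability.
- Section 5.5: treatment-related SAEs.
- Sections 6.4.3.1 and 6.4.4: SAEs in the 28-day follow-up period, regardless of causality.
- SAP section 4.3.1: treatment-emergent AEs run to 28 days after last dose, with no relatedness condition on events in that period.
- SAP section 5.7.1: deaths summarised from first dose to 28 days after last dose, if the data allow.

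Section 5.5 is the outlier.

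**4. What falls in the gap.** First, any SAE in the 28 days that the investigator calls unrelated. Second, deaths not attributed to treatment. Protocol section 6.4.3.2 keeps deaths unequivocally due to progression out of SAE reporting and documents them elsewhere in the CRF, so an SAE-only instruction would not pick them up. Section 5.3 names them explicitly.

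**5. Duration.** Three things are undetermined:

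- Section 5.1.7 gives two end points joined by *or*, and does not say whether the earlier or the later applies.
- It does not say where market availability is to be judged, in a study run in several countries.
- It counts from study completion, a term not defined beside the Appendix E definition of the end of the study that 5.5 appears to use.

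Section 5.5 then sets conditions for continuing without saying whether they operate inside the 5.1.7 bound or in place of it.

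**6. When the time limb could bite.** Section 5.4 puts the last planned cut-off 12 to 24 months after the last patient is enrolled. If that cut-off is taken as study completion (an assumption), the 2-year limb falls 12 + 24 = 36 to 24 + 24 = 48 months after the last enrolment, and later still after enrolment for earlier patients. The documents give no distribution of time on treatment, so the number of patients reaching it cannot be derived. The market limb has no date at all.

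**The case against.** The strongest reply on safety is that 5.5 does not claim to override anything. Sections 6.4.3.1 and 6.4.4 stand, and section 6.4.3.2 has its own rule for deaths in the follow-up period. A site that follows the general sections would report everything. Section 6.4.3.2 also already uses a related-only rule for SAEs learned of after a patient has completed the study, so the wording in 5.5 has a precedent. The first part stands to this extent: missing events are a possibility that depends on sites following 5.5 alone, not a certainty. A reader might infer that the addendum will undercount, or that unrelated SAEs go unrecorded throughout post-study treatment. The text supports neither, because on-treatment monitoring continues and the restriction covers only the 28 days after the last dose. The precedent is weak: it concerns events that come to light after completion, whereas patients under 5.5 are still being dosed and have a planned follow-up window.

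On duration, the reply is that silence is not contradiction. Section 5.1.7 can be read as the outer bound and 5.5 as the conditions for access inside it, so both can be obeyed. That reading is open, but no cross-reference establishes it. A reader might infer that 5.5 grants drug without limit; it does not, since benefit, sponsor-physician agreement and re-consent are all required. A reader might also infer that launch in any country stops supply everywhere, or that responders lose the drug at that point. Section 5.1.7 says nothing about place, and market availability could equally mean a move to commercial supply.

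**Conclusion.** The safety limb holds. Section 5.5 is narrower than sections 5.3, 6.4.3.1 and 6.4.4 for the same 28 days, and a patient dosed past both database lock and the end of the study is subject to conflicting collection rules. The consequence is that SAEs judged unrelated, and deaths, in that window can be lost from the CSR addendum if sites take 5.5 at its word.

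The duration limb also holds, but more softly: the two sections are unreconciled, not flatly opposed, and 5.1.7 is ambiguous even taken alone.

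The size is modest. Exposure to the problem is confined to patients still on drug at the end of the study. It is tempting to put a percentage on this by assuming a median time on treatment, but the documents supply none. A share counted from each patient's first dose would also measure the wrong interval, since the time limb runs from study completion. The primary ORR analysis, alpha and power are untouched.

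**What to change.** 1. In section 5.5, replace the treatment-related restriction with the scope of sections 5.3 and 6.4.4: all SAEs and all deaths, for 28 days after the last dose. Cross-refer to those sections so that the list is kept in one place.
2. Reconcile sections 5.1.7 and 5.5 on when post-study treatment ends. The text should say whether 5.5 is subject to 5.1.7, which of the two end points governs, and how market availability is determined. It should use one defined term for study completion or end of study. This review does not propose which rule to adopt.
3. Bring the consent and re-consent text into line with the result.

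The cost is protocol and consent wording. The 28-day window and the telephone contact in section 6.3.6.1 already exist, so the added burden is the reporting of SAEs judged unrelated, and deaths, for the few weeks after each such patient stops. The SAP's 28-day definitions need no change.
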